H1: Repeated bouts of exercise will continue to stimulate an acute catabolic response with an increase in bone resorption, as demonstrated by significant increases in serum CTX from before to after exercise in the 1st, 8th, and 16th exercise sessions.

SA2: Determine whether repeated exercise-induced increases in PTH generate an anabolic skeletal response over time, similar to the anabolic response to pharmacologic PTH analogs (teriparatide, abaloparatide). This will be evaluated by measuring the change in a serum marker of bone formation (i.e., increase in serum procollagen type 1 N-terminal propeptide; **P1NP**) from the 1st to the 16th exercise session.

H2: Exercise-induced increases in PTH will generate a chronic anabolic response in bone, as demonstrated by an increase in pre-exercise serum P1NP from the 1st to the 16th exercise session.

If the results of the POC phase **support H1** (significant catabolic responses) and **refute H2** (non-significant anabolic response), we will proceed to the RCT to determine whether Ca supplementation before exercise can attenuate the catabolic skeletal response and enhance skeletal adaptations to training.

Research Methods

A. Outcome Measure(s): Change in CTX from before to after exercise, Change in pre-exercise P1NP from 1st to 16th exercise session.

B. Description of Population to be Enrolled:

Participants. We will enroll female and male Veterans aged 25 to 45 y or 55 to 75 y. Eligible volunteers will be normally active (e.g., recreational cycling or walking) but will not participate in regular moderate-to-vigorous exercise. Women will be premenopausal with regular menstrual cycles or postmenopausal, defined as

absence of menses for at least 12 mo or, in those who underwent a hysterectomy, a serum follicle stimulating hormone (**FSH**) >30 mIU/mL.

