**Principal Investigator: [name]**

**Version Date: 03/03/2025    NCT ID: NCT05029128**

## **Data Analysis Plan**

The primary outcome for **Aim 1** is the change in CTX ( $\Delta\text{CTX}$ ) from before exercise to the peak value observed during 4 h of recovery, measured during the 1st, 8th, and 16th exercise sessions. The primary hypothesis is that there will be a significant  $\Delta\text{CTX}$  for all three exercise sessions. The changes will be tested based on a repeated measures model to test the statistical hypotheses  $H_0: \Delta\text{CTX}_j=0$  vs  $H_1: \Delta\text{CTX}_j \neq 0$ , where  $j$  denotes the exercise session. A single test will be conducted based on  $\Delta\text{CTX}_j$ , and differences and dependency across measures will be accounted for using an unstructured covariance matrix. This will enable testing of a single hypothesis to make decisions regarding  $\Delta\text{CTX}$ .

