**Power (Aim 1):** Attrition in our previous studies has been minimal (<10%), we have accounted for 20% attrition. The plan to enroll 30 participants (based on Aim 2) will ensure >99% power to address the hypothesis for Aim 1 in the full cohort and will also support secondary analyses of the sex specificity of the response. Based on our previous studies of older adults,  $\Delta\text{CTX}$  is expected to be 0.15 ng/mL and the standard deviation (**SD**) is expected to be 0.12 ng/mL, which corresponds to a standardized effect size of 1.25 (Cohen's  $d=1.25$ ). With statistical significance defined as  $p \leq 0.05$ , a sample size of 24 for a paired t-test will provide >99% power. Alternatively, with 90% power, we will be able to detect an effect size of 0.69. In addition, because the test will utilize a repeated measured model, it will have higher power than the paired t-test. The goal is to enroll 15 women and 15 men and expanding the age range to include Veterans aged 25 to 45 y will enhance the recruitment of women Veterans. We have not observed sex differences in the CTX response to exercise in previous studies, so an imbalance in sex should not influence the results. Our expectation is that the increase in serum CTX that we and others have observed in response to 1 or 2 exercise session in participants across a wide range of fitness (young, older, normally active, highly trained) will occur during the 1st, 8th, and 16th exercise sessions. A single test across all three time points will provide more power than multiple paired t-tests to evaluate the change in CTX at these time points. A significant test will be interpreted as evidence that exercise has an acute *catabolic* effect on bone that persists with exercise training.

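### A single overall test of ΔCTX is read as proof that the response persists, but it cannot show a response at each of sessions 1, 8 and 16

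*SAP*

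**What the plan says.** The Protocol (Specific Aims and Hypotheses for the POC Phase) words H1 as a continuing catabolic response, "as demonstrated by significant increases in serum CTX from before to after exercise in the 1st, 8th, and 16th exercise sessions". The SAP's Data Analysis Plan also expects a significant ΔCTX "for all three exercise sessions. The changes will be tested based on a repeated measures model". Both are statements about every session.

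The endpoint at each session is the change in CTX "from before exercise to the peak value observed during 4 h of recovery". The SAP then sets up one two-sided test of ΔCTX_j = 0, with j indexing sessions, in which "differences and dependency across measures will be accounted for using an unstructured covariance matrix". It explains: "This will enable testing of a single hypothesis to make decisions regarding" ΔCTX. It gives neither a contrast nor degrees of freedom.

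Power (Aim 1) is computed for one paired t-test. The paragraph adds that "because the test will utilize a repeated measured model, it will have higher power than the paired t-test", and that "A single test across all three time points will provide more power than multiple paired t-tests". It closes with the interpretation rule: "A significant test will be interpreted as evidence that exercise has an acute" catabolic effect on bone that is maintained as training continues.

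Two decisions use the result. The SAP tests P1NP (Aim 2) only if Aim 1 is significant. The Protocol proceeds to the RCT if H1 is supported and H2 is refuted. Change in the response from session to session is examined only in the SAP's secondary mixed model.

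**The concern.** The hypothesis is a conjunction: session 1 and session 8 and session 16. The complement of the tested null is a disjunction: at least one session mean differs from zero, in either direction. A test of the average has the same gap, because one or two responding sessions can carry it.

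This matters because the session 1 response is the part already expected. The SAP bases its expectation on earlier studies of one or two exercise sessions. What Aim 1 adds is whether the response is still there at sessions 8 and 16, and the planned test can be significant on session 1 alone. A response that had disappeared could be reported as persistent, and one of the two conditions for the RCT would be counted as met when it was not.

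**Working it through.** **Inputs from the SAP, Power (Aim 1).** Mean ΔCTX 0.15 ng/mL, SD 0.12 ng/mL, n = 24, two-sided alpha 0.05. The between-session correlation ρ is not given, so I assume it is equal for all pairs of sessions and vary it from 0 to 0.9.

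**The SAP's own figures.** d = 0.15/0.12 = 1.25. For a paired t-test with 23 df and noncentrality d√24, power at d = 1.25 is 99.995%. Power at d = 0.69 is 89.9%, and 90% power is reached at d = 0.691. Enrolment is 24/(1 − 0.20) = 30. All reproduce, but for one session's t-test.

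**Two readings of the single test.** Let δ be the vector of standardized session means and R the correlation matrix.

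- *Joint 3-df test:* F(3, 21) with noncentrality 24·δ′R⁻¹δ. With session 1 only, this is 24 × 1.25² × (1 + ρ)/[(1 − ρ)(1 + 2ρ)] = 37.5 at ρ = 0 and 56.25 at ρ = 0.5. With all three responding, it is 112.5/(1 + 2ρ).
- *1-df average:* a one-sample t-test with effect size (sum of δ / 3)/√[(1 + 2ρ)/3]. With session 1 only, this is 0.722 at ρ = 0 and 0.431 at ρ = 0.9.

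Probability of a significant result at n = 24:

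| ρ | Joint, session 1 only | Average, session 1 only | Average, sessions 1 and 8 only | Joint, all three |
|---|---|---|---|---|
| 0 | 99.87% | 92% | >99.9% | >99.9% |
| 0.25 | 99.95% | 79% | >99.9% | >99.9% |
| 0.5 | >99.9% | 67% | 99.8% | >99.9% |
| 0.8 | >99.9% | 56% | 98.7% | >99.9% |
| 0.9 | >99.9% | 53% | 98.1% | >99.9% |

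The joint test with sessions 1 and 8 only also exceeds 99.9% throughout. It barely distinguishes a response lost after session 1 from one present at all three.

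**The per-session rule.** This requires all three t-tests to be significant at two-sided 0.05 and positive. By simulation with n = 24 and ρ from 0 to 0.9:

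- All three at d = 1.25: power about 99.98%.
- Session 1 only, others centred at zero: H1 declared in 0.06% (ρ = 0) to 1.4% (ρ = 0.9).
- Sessions 1 and 8 only: about 2.5%.
- All three at d = 0.69: power 73% (ρ = 0) to 85% (ρ = 0.9). Power of 90% needs d of about 0.81 (ρ = 0) to 0.75 (ρ = 0.9).

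**The higher-power sentence**, with d = 0.69 at all three sessions, against 89.9% for the paired t-test:

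| ρ | Joint 3-df | Average |
|---|---|---|
| 0 | 99.7% | 99.99% |
| 0.25 | 96.7% | 99.6% |
| 0.5 | 90.0% | 97.7% |
| 0.8 | 80% | 93.5% |
| 0.9 | 77% | 91.8% |

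**Effect of the peak endpoint.** The largest of several noisy values minus one baseline value is positive on average even without a response. The recovery sampling times are in a figure not shown, so I assume independent, equal noise. With 2, 3 or 4 recovery samples the standardized ΔCTX under no response is 0.43, 0.68 or 0.84. The chance that both sessions 8 and 16 then have a CI above zero is about 28%, 79% or 96%. These values are illustrative; correlated noise or a drifting baseline would change them.

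**The case against.** **The size depends on the reading.** A reader might infer that the planned test rejects almost surely whatever happens after session 1. The documents do not support that without qualification. It is true of a joint 3-df test at the planned effect. The SAP's wording also allows a three-session average, for which the figure is 53–92%. At half the planned effect at session 1, even the joint test falls to 64% at ρ = 0. The inference from significance to persistence fails under every reading; only its frequency changes.

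**The power sentence is not simply false.** It is correct for an average at every correlation examined. It fails for a joint test only when ρ exceeds about 0.5, and no correlation is given.

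**There is some protection elsewhere.** The SAP's secondary mixed model estimates how responses change from session 1 to 8 to 16, and the SAP says that secondary analyses may help guide the RCT decision. This mitigates the problem but does not cure it, because no rule is attached. The RCT also requires H2 to be refuted, and P1NP is still tested at 0.05, so opening Aim 2 wrongly does not by itself inflate that test's error. A reader might also take absence of attenuation as a requirement of H1. It appears only in the Protocol's introductory description of the catabolic-only option.

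**The replacement rule has a limit.** Its low false-persistence rates assume that ΔCTX averages zero without a response, and a baseline-to-peak measure does not ensure this. That objection stands and shapes the fix.

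**Conclusion.** The Aim 1 decision rule is wrong as written. It answers whether any session (or the average) shows a change, and reports the answer as a response at every session. At n = 24 and d = 1.25, with session 1 alone responding, the false reading occurs at least 99.8% of the time for a joint test and 53–92% for an average. If only session 16 has lost the response, it occurs at least 98% of the time on either reading. These figures assume equal between-session correlations of 0–0.9, the SAP's SD at each session, and a mean ΔCTX of zero where there is no response.

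It would go too far to infer that the per-session rule guarantees false-persistence rates of about 1.5% and 2.5%. The peak endpoint is biased upward by noise, so those rates hold only under the zero-mean assumption.

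**What to change.** - Keep the repeated-measures model with unstructured covariance. Declare H1 supported only if the two-sided 95% CI for ΔCTX lies above zero at each of sessions 1, 8 and 16. This is an intersection-union test, so each session is tested at 0.05 with no alpha penalty. Use this result for the Aim 2 gate and the RCT condition.
- Report session 16 minus session 1 with its CI beside that decision. Similar peak bias at the two sessions largely cancels in this contrast.
- Add a sensitivity analysis that repeats the rule with ΔCTX at a fixed recovery time, or as mean recovery minus baseline, from samples already collected. Do not quote the 1.5% and 2.5% rates as guaranteed.
- Restate Aim 1 power for this rule: above 99% at d = 1.25, and 90% at d of about 0.75–0.81 depending on correlation, in place of 0.69.
- Remove the statement that the repeated-measures test has more power than the paired t-test, or qualify it by the contrast and correlation assumed.

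The cost is SAP wording, one added analysis and a less favourable detectable effect. Power at the planned effect stays above 99%, and enrolment of 30, which the SAP bases on Aim 2, does not change.

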The main outcome for **Aim 2** is the change in pre-exercise serum P1NP ( $\Delta\text{P1NP}_{\text{PRE}}$ ) from the 1st to the 16th exercise session. If the exercise-induced increase in PTH is anabolic, the pre-exercise P1NP values are expected to increase over the 16 exercise bouts, just as basal P1NP increases in response to PTH analog therapy (Fig 12-14). The observed change will be tested using a 2-sided paired t-test to test the statistical hypotheses  $H_0: \Delta\text{P1NP}_{\text{PRE}}=0$  vs  $H_1: \Delta\text{P1NP}_{\text{PRE}} \neq 0$ . This test will be conducted only if the test for Aim 1 is significant. The relative increase in P1NP after 4 wk of teriparatide or abaloparatide therapy ranged from 80% to 138% in several studies, and estimated effect sizes ranged from 1.3 to 2.6. We will take a conservative approach to finding an anabolic signal with exercise and use an effect size that is 53% smaller than the smallest effect size for change in P1NP in response to teriparatide or abaloparatide (0.69). Under these conditions, a sample size of 24 will enable us to detect a change in  $\Delta\text{P1NP}_{\text{PRE}}$  from the 1st to the 16th exercise session with 90% power. We will enroll 30 Veterans to allow for 20% attrition.

We considered correcting the significance level (alpha) for multiple tests because we are conducting two tests in the POC study (CTX, P1NP). However, because the second hypothesis test of P1NP will be conducted only if the first hypothesis test of  $\Delta\text{CTX}$  is significant and a hierarchy of tests has been defined *a priori*, we chose to not correct the significance level.

The distributions of the outcome measures will be evaluated. All analyses will be performed using SAS 9.4 software (SAS Institute Inc., Cary, NC). If there are severe departures from a normal distribution, transformations (e.g., natural logarithm) will be applied as appropriate to achieve an endpoint that seems normally distributed. To minimize missing data, all participants will be informed of the importance of complete follow-up and encouraged to complete the study per the protocol. We will make substantial efforts to prevent missed exercise tests and samples. Monthly reports will be generated that summarize recruitment, accrual, and completeness of follow-up to allow research assistants to proactively follow-up with participants in a timely

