manner. Prior to beginning analyses described below to address study hypotheses, we will examine the data carefully to assess whether patterns of missing seem ignorable (MAR=missing at random) or non-ignorable (MNAR= missing not at random). If the former, we will employ likelihood-based methods that utilize all available data, adjusting for covariates that are associated with missingness. If missingness seems non-ignorable we will consider, as data permit, pattern mixture models. Sensitivity analyses may be carried out using multiple imputation approaches.

The primary analyses for Aims 1 and 2 utilize only a portion of the data that will be collected. Secondary analyses will take advantage of the rich data set generated during the POC phase and can be used to help guide decision-making for the RCT. A linear mixed model based on maximum likelihood with all available data will be conducted to evaluate changes in CTX, P1NP, and other secondary outcomes (iCa, tCa, PTH, PO4, Hct, urinary Ca excretion) during exercise and recovery and how responses change from the 1st to the 8th to the 16th exercise session. Secondary analyses will also be conducted to investigate, for example, whether responses are influenced by age, sex, bone turnover marker level at baseline, or absolute exercise intensity. Interaction terms of treatment variable and variable of interest will be included to test for heterogeneity of treatment effect.

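### The SAP picks the missing-data method by judging MAR against MNAR from the data, and does not say whether that rule or the named paired t-test governs Aim 2

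*SAP*

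**What the plan says.** All SAP text cited here is in the Data Analysis Plan.

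- **Aim 1.** A repeated measures model of the CTX change at sessions 1, 8 and 16, in which "differences and dependency across measures will be accounted for using an unstructured covariance matrix".
- **Aim 2.** The outcome is the change in pre-exercise P1NP from session 1 to session 16: "The observed change will be tested using a 2-sided paired t-test to test the statistical hypotheses". The SAP gives 90% power with 24 participants at an effect size of 0.69, and enrols 30 to allow for 20% attrition.
- **Missing data.** The rule opens "Prior to beginning analyses described below to address study hypotheses" and continues "we will examine the data carefully to assess whether patterns of missing seem ignorable (MAR=missing at random) or non-ignorable". If ignorable, "we will employ likelihood-based methods that utilize all available data, adjusting for covariates that are associated with missingness". If not, "If missingness seems non-ignorable we will consider, as data permit, pattern mixture models". Finally, "Sensitivity analyses may be carried out using multiple imputation approaches".
- **Secondary analysis.** A maximum likelihood mixed model using all available data covers P1NP across the three sessions.

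The protocol (section C.3) collects pre-exercise blood at sessions 1, 8 and 16. Section C.2 defines compliance as at least 75% of sessions, which is 12 of 16, so a compliant participant may have no 16th session. Under Hypotheses and Specific Aims, the RCT follows only if the CTX response is significant and the P1NP change is not. Neither document defines an analysis set for Aim 2.

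**The concern.** There are two linked problems.

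First, MAR and MNAR differ only in how missingness depends on values that nobody observed. The data can argue against missingness completely at random, but they cannot say which of the other two holds. A rule that branches on which one seems true therefore has no evidential basis. No criterion, covariate list or pattern definition is fixed in advance, and the sensitivity analysis that should carry this uncertainty is optional and names no MNAR assumption.

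Second, the branch for ignorable missingness and the Aim 2 test are different analyses. A paired t-test drops anyone lacking either end value, even when session 8 was measured. The likelihood branch keeps them.

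The Aim 2 result is a gate. If participants with smaller P1NP changes leave, the completers' mean is too high and the RCT could be stopped by a false anabolic signal. If participants with larger changes leave, a real signal could be missed and the RCT could proceed on that basis.

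**Working it through.** **1. The plan's own figure.** Paired t-test, two-sided alpha 0.05, n = 24, effect size 0.69, noncentral t with 23 df and noncentrality 0.69 × √24 = 3.38: power 0.899. Enrolment: 24 / (1 − 0.20) = 30. Both reproduce.

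**2. Who is lost.** At 20% attrition, 0.20 × 30 = 6 participants leave the Aim 2 test. At 10% (the SAP reports under 10% in previous studies), 3 leave.

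**3. Size of the bias, under assumptions.** The documents give no dropout mechanism, so these inputs are assumed:

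- The SD of the session 1 to 16 change is set to 1.
- P1NP at any two sessions is equally correlated (0.7 or 0.85). The session 1 to 8 and session 1 to 16 changes then correlate at 0.5, whichever value is used.
- Dropout follows a latent score that correlates g with the session 1 to 8 change, and the lowest scorers leave.

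The completers' mean is then biased by k × g × 0.5, where k is the mean of the retained scores. For the top 24 of 30 standard normal values k = 0.338; for the top 27 of 30, k = 0.186. The SE is 1/√24 = 0.204 or 1/√27 = 0.192. Upper-tail error is approximately P(Z > 1.96 − bias/SE).

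| g | 6 lost: bias (SD) | upper tail | 3 lost: bias (SD) | upper tail |
|---|---|---|---|---|
| 0 | 0 | 2.5% | 0 | 2.5% |
| 0.3 | 0.05 | 4% | 0.03 | 3% |
| 0.5 | 0.08 | 6% | 0.05 | 4% |
| 0.7 | 0.12 | 8% | 0.07 | 5% |
| 0.85 | 0.14 | 11% | 0.08 | 6% |

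For example, at g = 0.85 with 6 lost: 0.338 × 0.85 × 0.5 = 0.144; 0.144 / 0.204 = 0.70; P(Z > 1.26) is about 10.5%. Simulation with 20,000 runs per cell agrees (0.141 to 0.146 SD, about 11%). If the highest scorers leave, the bias has the same size and the opposite sign.

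**4. What session 8 recovers.** In the same simulations, a likelihood estimate using sessions 1, 8 and 16 has bias of about 0 with SE 0.20 to 0.21 when all 6 dropouts have session 8 data. If the half most prone to leave go before session 8, about 0.02 to 0.07 SD remains. With outcome-unrelated dropout its variance is only about 4% to 5% smaller.

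**5. What no MAR method removes.** If dropout correlates 0.3 to 0.7 with the unseen session 16 change itself, the completers' bias with 6 lost is 0.338 × 0.3 = 0.10 to 0.338 × 0.7 = 0.24 SD, and session 8 data can recover only part of it. This is the case for a required MNAR sensitivity analysis.

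**The case against.** Several points on the other side stand.

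- **The tests are named in advance.** The missing-data paragraph speaks of analyses that come after it, and what follows it is the secondary analyses. A reader might infer that the estimator behind the RCT decision is left to a post hoc call. The documents do not establish that. The same sentence also refers to addressing the study hypotheses, so its reach is unclear rather than settled either way.
- **Selection on P1NP is not documented.** A reader might infer that the paired t-test is known to be biased. Under protocol section C.3, a participant's samples from all three sessions are stored and assayed together, so neither participant nor staff would know the session 8 P1NP when someone leaves. An indirect link, such as illness or injury affecting both, is possible but would normally be weak. That points to the lower rows of g.
- **Attrition of 20% is a planning margin.** Previous attrition was under 10%, the protocol allows up to two extra weeks to finish 16 sessions, and the SAP plans active prevention of missing samples. The 3-lost columns may be the more realistic ones.
- **Much of the remedy is already planned.** The mixed model for P1NP exists as a secondary analysis, and Aim 1 already has a repeated measures model.

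These points reduce the likely size. They do not make MAR and MNAR distinguishable, and they do not settle which instruction governs Aim 2.

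**Conclusion.** The point holds as a defect of specification that should be corrected before the data are analysed. Two conclusions need no assumption: the branching rule asks the data a question they cannot answer, and its likelihood branch conflicts with the complete-case test named for Aim 2 without an order of precedence.

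The numerical effect is conditional. With dropout unrelated to P1NP change, the paired t-test is valid. With the assumed selection on the session 1 to 8 change (g from 0.3 to 0.85), bias is about 0.05 to 0.14 SD and upper-tail error about 4% to 11% with 6 of 30 lost, and about 0.03 to 0.08 SD and 3% to 6% with 3 lost. These are illustrations, not forecasts. The likelihood model is also not unbiased in all cases: it removes the bias under MAR only to the extent that dropouts have session 8 data.

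**What to change.** - **Aim 2 primary model.** Name one in advance: a REML repeated measures model of pre-exercise P1NP at sessions 1, 8 and 16, with unstructured covariance, Kenward-Roger degrees of freedom and the session 16 minus session 1 contrast, in all enrolled participants with a baseline value. With complete data it returns the paired t-test estimate. Name any covariates in advance.
- **Selection rule.** Delete the text that chooses the primary method from a MAR/MNAR assessment.
- **Sensitivity.** Make one MNAR analysis, delta-adjusted or pattern-mixture, a required sensitivity analysis.
- **Aim 1.** Keep the repeated measures model already specified and remove only the data-driven switch.

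The cost is SAP wording and a few lines of SAS. No new data are needed, the SE is about the same, and the 24 evaluable and 30 enrolled are unchanged.

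### Maximum likelihood for the secondary mixed models makes standard errors 2% to 9% too small at n = 24, and the Aim 1 joint test over-rejects modestly unless a small-sample correction is named

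*SAP*

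**What the plan says.** All of this is in the SAP, Data Analysis Plan.

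- **Secondary analyses.** The estimator is named: "A linear mixed model based on maximum likelihood with all available data will be conducted". These models cover CTX, P1NP and other outcomes during exercise and recovery and across sessions 1, 8 and 16. Age, sex, baseline bone turnover and absolute intensity are given as examples of possible modifiers, tested through interaction terms. The covariance structure is not stated. The SAP says the results may help guide decisions about the RCT.
- **Aim 1.** One test covers the change in CTX at the three sessions, and "differences and dependency across measures will be accounted for using an unstructured covariance matrix". The stated reason for a single test is that "A single test across all three time points will provide more power than multiple paired t-tests". Neither ML nor REML is named for this model.
- **Missing data.** If missingness looks ignorable, "we will employ likelihood-based methods that utilize all available data".
- **Aim 2.** "The observed change will be tested using a 2-sided paired t-test", and only if the Aim 1 test is significant. The SAP uses this ordering to justify not adjusting alpha.
- **Size.** 30 enrolled and 24 analysed, on the basis that "a sample size of 24 for a paired t-test will provide >99% power".

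The software is SAS 9.4. Neither document mentions REML, a denominator-df method or any other small-sample correction.

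**The concern.** There are two separate issues.

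First, ML estimates variances without allowing for the mean parameters fitted. With several hundred people this is harmless. With 24 to 30 people it shortens every standard error, and more so as between-subject terms such as sex or age group are added, which the SAP plans to do.

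Second, a joint test of several means on an estimated unstructured covariance has a heavier-tailed null distribution than chi-square or F with n-1 denominator df. This is true under REML as well as ML, so changing the estimator alone does not cure it.

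The first issue affects analyses that may inform the RCT. The second affects the primary Aim 1 test. That test is the gate for Aim 2, and the argument for leaving alpha unadjusted assumes that the gate holds its nominal 5%.

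**Working it through.** **Inputs from the SAP.** n = 24 analysed and 30 enrolled; two-sided alpha 0.05; three sessions; planned change 0.15 ng/mL with SD 0.12, so d = 1.25; detectable d = 0.69 at 90% power.

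**The plan's own figures.** For a paired t-test with n = 24, the noncentrality is d × √24 and the critical value is t(0.975, 23) = 2.069.
- d = 1.25: noncentrality 6.12, power 99.995% (stated >99%).
- d = 0.69: noncentrality 3.38, power 89.9% (stated 90%).
- Enrolment: 24 / (1 - 0.20) = 30.

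All three reproduce. The documents give no type I error figure for the mixed models.

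**Step 1: ML standard errors, single contrast.** With g between-subject mean parameters and complete data, the ML standard error is √((n-g)/n) times the unbiased one. The ML statistic is too large by the inverse of that ratio. Referred to t with the correct n-g df, the actual size is P(|t(n-g)| > ratio × critical value).

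| n | g | SE ratio | SE too small by | Effective critical value | Size |
|---|---|---|---|---|---|
| 24 | 1 | 0.979 | 2% | 0.979 × 2.069 = 2.025 | 5.5% |
| 24 | 2 | 0.957 | 4% | 0.957 × 2.074 = 1.986 | 6.0% |
| 24 | 4 | 0.913 | 9% | 0.913 × 2.086 = 1.904 | 7.1% |
| 30 | 1 | 0.983 | 2% | 0.983 × 2.045 = 2.011 | 5.4% |
| 30 | 2 | 0.966 | 3% | 0.966 × 2.048 = 1.979 | 5.8% |
| 30 | 4 | 0.931 | 7% | 0.931 × 2.056 = 1.914 | 6.7% |

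Here g = 1 is simple session means, g = 2 adds one two-level factor such as sex, and g = 4 is a full age-group-by-sex model.

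**Step 2: Aim 1 joint test.** I read the single test as 3 df, all three session means equal to zero. With complete data and an unstructured covariance, the REML Wald statistic is Hotelling's T², distributed as [p(n-1)/(n-p)] × F(p, n-p). The ML statistic is T² × n/(n-1).

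For p = 3 and n = 24 the multiplier is 3 × 23 / 21 = 3.286. With F(3, 23) as the assumed reference, rejection needs a statistic above 3 × 3.028 = 9.084.
- REML: 9.084 / 3.286 = 2.765, and P(F(3, 21) > 2.765) = 6.7%.
- ML: 2.765 × 23/24 = 2.650, which gives 7.5%.

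The chi-square reference (7.815) is worked in the same way.

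| Reference | REML, n = 24 | ML, n = 24 | REML, n = 30 | ML, n = 30 |
|---|---|---|---|---|
| F(3, n-1) | 6.7% | 7.5% | 6.3% | 7.0% |
| chi-square, 3 df | 9.9% | 10.9% | 8.7% | 9.5% |
| exact F(3, n-3), rescaled | 5.0% | 5.7% | 5.0% | 5.5% |

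The ML likelihood-ratio test gives 7.2% and 6.7% at the two sample sizes.

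A simulation with dropout tells the same story. It used ML, 4,000 runs, 30 enrolled, 24 complete, three people with session 1 only, three with sessions 1 and 2, and an assumed correlation of 0.5. Size was 7.6% (F, 29 df) and 10.1% (chi-square), and model standard errors were 3% to 5% below the empirical SD.

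If the single test were instead a 1-df test of the average change, REML with n-1 df would be exact and ML would give 5.5% at n = 24.

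**Step 3: power after correction.** With the exact F(3, 21) reference, n = 24 and d = 1.25 at every session, power is above 99.9% for assumed between-session correlations from 0 to 0.8.

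**The case against.** The strongest reply is that the SAP never puts ML and an unstructured covariance in the same model. ML belongs to the secondary models, and the unstructured covariance belongs to Aim 1. That is correct, and the two issues are kept apart here for that reason.

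It also limits the claim. A reader might infer that the secondary joint tests have type I error of 12% to 31%. At n = 24 those figures do arise for an unstructured covariance with n-1 df: 12% (REML) or 14% (ML) at 6 df, and 28% or 31% at 10 df. The SAP states neither condition for those models. Fitting the full set of draws that way would also be impossible with 24 completers. The Protocol (section C.3) lists two pre-exercise draws, four during exercise, at least one in recovery and one at 24 h, so at least 8 × 3 = 24 measures per person against 23 residual df. Under compound symmetry the ML size at n = 24 is about 6% with matching within-person df (6.0% at 6 df, 6.3% at 10 df). With n-1 df it is 2% to 3%, which is conservative.

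Three further replies have force. The SAP is silent on df and does not exclude a correction. The 7.1% figure needs a four-cell age-by-sex model, whereas the SAP lists age and sex only as separate examples. And no key decision is shown to change: at d = 1.25 the Aim 1 conclusion would hardly move, and the Aim 2 paired t-test is untouched.

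What remains is that ML is an explicit choice for a small sample, and that none of the uncorrected references considered for a 3-df Aim 1 test holds 5%.

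**Conclusion.** The point holds as a minor one. At n = 24 the stated ML estimation makes secondary standard errors 2% to 9% too small, with single-contrast type I error of 5.5% to 7.1% depending on the between-subject terms. At n = 30 the error is 5.4% to 6.7%. The Aim 1 test, if it has 3 df and no correction, has size 6.7% to 10.9% at n = 24 across the estimators and references considered. Most of that excess comes from the reference distribution, not from ML.

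These figures assume normal data and, outside the simulation, complete data. The n-1 df and chi-square references are assumptions, because the SAP names none. Severe inflation in the secondary joint tests cannot be concluded from the documents, since their covariance structure is not given.

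**What to change.** In the secondary-analysis paragraph, replace maximum likelihood with REML and Kenward-Roger degrees of freedom. State the same for the Aim 1 repeated-measures model (in SAS, METHOD=REML and DDFM=KR). Reserve ML for comparing models with different mean structures. In the same sentence, name the covariance structure of the secondary models and say that the Aim 1 test is a 3-df test, if that is the intention.

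REML is itself likelihood-based and uses incomplete records, so the missing-data approach stands. The cost is one or two SAP sentences, two software options and slightly wider intervals. Neither the sample size nor the Aim 2 test needs to change.
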